7.4.4 Clinical Data Capture

Upon receiving and reviewing completed Stage 2-specific ICF, the study team will review patient medical records and capture required data for the following eCRFs:

Cancer Medical History: capturing data regarding, time since cancer diagnosis, cancer stage, primary or secondary cancer, surgery type, neoadjuvant or adjuvant treatment, and positivity for oestrogen receptors (ER), progesterone receptors (PR) or human epidermal growth factor receptor 2 (HER2).

Cancer Treatment: current breast cancer treatment broken down by chemotherapy, radiotherapy, and hormonal therapy and information regarding current medication cycle.

Current Co-morbidities: current co-morbidities and whether each co-morbidity is being treated with medication.

7.4.5 End of Study Procedures

At day 21 of follow up, the ePRO module of the eCRF will automatically send by text message (or email, if required) each participant in Stage 2 of the study the End of Study Questionnaire set consisting of:

- ISI
- EQ-5D-5L
- FACT-ES
- User experience questionnaire (UEQ)

The participant can complete the questionnaires on their smartphone. It is estimated the participant will take 20-25 minutes to complete these questionnaires. If the questionnaire set is not completed by the participant within 3 days, the eCRF will send a questionnaire reminder email or text message. This will be repeated on two subsequent occasions if the questionnaire remains uncompleted within the three preceding days. Questionnaires can also be completed on computer or tablet however smartphone completion is preferred.

On day 21 (+8 days), a member of the clinical study team will phone each participant and record any AEs and SAEs that the participants have experienced in the previous 3 weeks. AE's and SAEs will be entered into the eCRF and patient health records. Prior to the phone call, the eCRF will be checked to determine if the participant has completed the End of Study Questionnaire set. If this has not been completed, the staff member will remind the participant to complete these questionnaires. The clinical study team will attempt to telephone the participants on three occasions. If unsuccessful, this will be recorded as a missed visit in the site protocol deviation log.

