To assess the feasibility and experience of patients with breast cancer to input data relating to their sleep into a mobile phone application daily.	Feasibility and experience of patients using the digital sleep diary will be assessed using the UEQ.	Performed at Day 21 on all participants enrolled in Stage 2. Participants who withdrew from the study will be offered the questionnaire.
To assess safety of patients using the digital sleep diary.	Numbers of AEs and SAEs.	Participants will be asked to report any AEs experienced during the three-week observational period at Day 21 in a telephone consultation with the study team.
To determine associations between severity of insomnia and clinical or treatment characteristics of breast cancer patients.	Assessment of insomnia prevalence, severity, and quality of life in subgroups based on clinical/treatment characteristics including breast cancer stage, treatment regime and baseline insomnia severity.	Performed on data collected at Stage 1 and across Stage 2.

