7 TRIAL PROCEDURES

Table 1. Assessment Schedule

Assessment/ Procedure	Stage 1		Stage 2		
	Screening (-14 days)	Day 0	Screening (-28 days) ⁵	Day 0	Days 1-21
Stage 1:					
Informed Consent ¹ for Stage 1 & Registration	x				
ISI ²		x			
EQ-5D-5L ²		x			
FACT-ES ²		x			
Demographics ²		x			
Sleep History ²		x			
Stage 2:					
Informed Consent for Stage 2 ¹			x		
Review Eligibility Criteria			x		
Cancer Medical History				x	
Current Cancer Treatment				x	
Current Co-Morbidities				x	
Digital Diary Download ³				x	
Daily Sleep Diary Entry ³					x
ISI ²					x
EQ-5D-5L ²					x
FACT-ES ²					x
UEQ ²					x
Adverse Events ⁴					x

¹ Where possible will be online remote eConsent but can be completed in clinic (online/paper).

² Participant completes online questionnaire (paper questionnaires will be available for clinic use).

³ Participants completes on their own smartphone.

⁴ AEs will be collected at follow-up telephone consultation at Day 21 (+8 days).

⁵ Stage 2 Consent should occur no later than 28 days post Stage 1 Consent, however ideally this would occur as soon as possible after consent for Stage 1 has been provided.

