9.2 Operational definitions for (S)AEs

The risks to participants enrolled in this observational study are considered very low.

All AEs and SAEs experienced during the three-week study period by participants enrolled in Stage 2 will be recorded in the eCRF and in the patients' medical records. AEs and SAEs can either be volunteered by the participant or detected by the clinical research team through physical examination or in the patients' medical notes.

Only SAEs that the Principal Investigator (PI) considers to be directly related to the digital sleep diary will be reported to the Sponsor via the EDC system.

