9.3 Recording and reporting of SAEs

For each AE, the investigator must pursue and collect information to adequately determine the outcome of the AE and to assess whether it meets the classification criteria of an SAE. All SAEs considered to be directly related to the digital sleep diary, occurring from the time of participant consent to Stage 2 of the study to the conclusion of the 3-week observation period, must be reported to the Sponsor within 24 hours of awareness of the event by the PI. In the rare situation that the PI does not become immediately aware of the occurrence of a safety event, the PI must report the event within 24 hours of learning about it and record the time of awareness of the event.

For each SAE, the following information will be collected: full details in medical terms and case description, event duration (start and end dates, if applicable), action taken, outcome, seriousness criteria, and causality (i.e. relatedness to the digital sleep diary), in the opinion of the PI. Any change of condition or other follow-up information should be updated in the EDC system. The Sponsor should be notified as soon as it is available or at least within 24 hours of the information becoming available. Events will be followed up until the event has resolved or a final outcome has been reached.

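### The adverse-event call may be made as late as day 29 with a three-week look-back not tied to the observation period, which conflicts with the fixed AE period stated elsewhere

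*Protocol*

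**What the plan says.** The operative instruction is in Protocol 7.4.5. On timing it states: "On day 21 (+8 days), a member of the clinical study team will phone each participant". For the content of the call, the look-back is set by telling the caller to "record any AEs and SAEs that the participants have experienced in the previous 3 weeks". Footnote 4 of Table 1, in both the Protocol and the SAP, repeats the 8-day allowance. Table 1 schedules AE collection once, at this contact.

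The other descriptions of the AE period use a fixed interval:

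- The endpoint table in Protocol 3.5 says that participants will be "asked to report any AEs experienced during the three-week observational period at Day 21", by telephone. The objectives table in SAP 1.1 uses the same wording.
- Protocol 9.2 sets the recording requirement: "All AEs and SAEs experienced during the three-week study period by participants enrolled in Stage 2 will be recorded in the eCRF". It also allows sources other than the call: "AEs and SAEs can either be volunteered by the participant or detected by the clinical research team".
- Protocol 9.3 sets a different window for reporting SAEs judged directly related to the diary, namely those "occurring from the time of participant consent to Stage 2 of the study to the conclusion of the 3-week observation period".

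SAP 3.5 summarises the number and percentage of patients with at least one AE, SAE or diary-related AE in the Stage 2 analysis set. It sets no limit on onset date.

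**The concern.** One call is given two recall periods. The period to be captured is fixed, but the section that staff would follow counts back three weeks without saying from which day. The ordinary reading is from the day of the call. The days covered would then depend on when the participant answers the telephone, and 7.4.5 foresees up to three attempts.

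Safety of diary use is a stated secondary objective (Protocol 3.2, item 4). If the moving window is applied, late-call participants contribute a different set of days from those called on day 21. Events early in diary use could go unasked, while events after the period could be counted. SAP 3.5 would not detect either, because nothing in it compares onset with the observation period. Protocol 9.3 asks for start and end dates for each SAE, but the documents state no such requirement for non-serious AEs.

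**Working it through.** No sample size or error rate is involved, so the check is a count of days.

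**Inputs.** The observation period is days 1 to 21 (Protocol 7.4.3 and Table 1). The call day c runs from 21 to 21 + 8 = 29 (Protocol 7.4.5; Table 1, footnote 4). The look-back is 3 × 7 = 21 days (Protocol 7.4.5).

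**Literal reading of 7.4.5.** The text does not say whether the call day counts, so three conventions were tried for the latest permitted call, c = 29:

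| Convention | Look-back | At c = 29 | Observation days missed | Later days added |
|---|---|---|---|---|
| 21 days ending on the call day | c − 20 to c | 9 to 29 | 1 to 8: 8/21 = 38% | 22 to 29: 8 |
| 21 full days before the call day | c − 21 to c − 1 | 8 to 28 | 1 to 7: 7/21 = 33% | 22 to 28: 7 |
| Both end days counted | c − 21 to c | 8 to 29 | 1 to 7: 7/21 = 33% | 22 to 29: 8 |

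With the first convention the number of days missed is c − 21: 0 at day 21, 4 at day 25 and 8 at day 29. With the other two, the number of early days missed is c − 22 from day 22 onward.

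**Average over calls.** The documents give no distribution of call days. If calls were spread evenly over days 21 to 29 (an assumption made only for scale), the mean number of early days missed would be (0 + 1 + … + 8)/9 = 36/9 = 4 days, or 4/21 = 19%, under the first convention. Under the other two it would be (0 + 0 + 1 + … + 7)/9 = 28/9 = 3.1 days, or 15%. If most calls fall on or near day 21, it is close to zero.

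**Reading of Protocol 3.5 and SAP 1.1.** The question covers days 1 to 21 whatever the call date. Observation days missed: 0 of 21 for every c from 21 to 29.

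**Window in Protocol 9.3.** It opens at Stage 2 consent, before day 1. A 21-day look-back from a call on day 21 reaches back only to day 0 or day 1, so this start lies outside the look-back even for a punctual call. The window governs only SAEs judged directly related to the diary.

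**The case against.** The best defence is that 7.4.5 is loose wording for the observation period just ended. Protocol 3.4 (item vii), Protocol 3.5 and SAP 1.1 all describe the same call in those terms, and a caller who knew them would ask about the right days. Protocol 9.2 requires the whole period to be recorded and allows events to be volunteered or found by examination or in the notes, so an event in the first week could still be captured. The schedule aims at day 21, which makes day 29 a limit and not the norm. SAP 3.5 expects few events, and it counts patients with any event, so missing days do not translate in proportion into missing counts.

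Much of this stands. A reader might infer from 7.4.5 that the call asks about nothing but the trailing three weeks and that the first 8 days are never asked about. The documents do not support that: 7.4.5 contains no such restriction, and two tables give the fixed period. A reader might also infer that the call should cover all AEs from Stage 2 consent. That is not supported either, because 9.2 sets AE recording to the three-week study period, and the consent start in 9.3 applies only to diary-related SAE reporting. Nor do the documents show that diary-related problems cluster at first use.

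What the defence does not remove is the conflict itself. The section that instructs staff carries the moving window. The other sources in 9.2 are a weak safety net in a study that requires no visits (Protocol 4) and does not monitor diary adherence during the three weeks (Protocol 8.5).

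**Conclusion.** The point holds as an inconsistency in the recall window, with a possible gap for late calls. The size depends on the reading. It is zero on the wording of Protocol 3.5 and SAP 1.1. On the literal wording of 7.4.5 it is at most 7 or 8 of 21 days (33% to 38%) for a call on day 29, with 7 or 8 out-of-period days added. The choice between 7 and 8 rests only on whether the call day counts. The averages of 15% to 19% rest on an even spread of calls, which no document supports.

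The consequence is confined to which AEs are counted for a secondary, descriptive outcome in a study that the Protocol rates as very low risk. The primary prevalence estimate is unaffected. It is still worth correcting, because the correction costs little and Table 1 schedules no second AE enquiry.

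**What to change.** 1. **Protocol 7.4.5 and any call script:** ask about AEs from diary day 1 to day 21, with both calendar dates pre-filled for each participant. SAP 2.4 already defines Stage 2 day 1 as the first day the diary is completed. A start date should also be named for a Stage 2 participant who makes no diary entry.
2. **eCRF:** record the onset date for all AEs, not only for SAEs.
3. **SAP 3.5:** count only AEs with onset from day 1 to day 21, and list later events separately.
4. **Protocol 9.3:** reconcile its window, which opens at Stage 2 consent for diary-related SAEs, with the AE period in 9.2, and say how events between consent and day 1 are to be identified.
5. **If the calls have already been made** (recruitment was planned to end by January 2022 and the SAP is dated September 2022): report the distribution of call days, state which look-back was used, and identify events with onset after day 21 where dates exist.

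The cost is a few sentences in each document, one date field if it is not already collected, and slightly longer recall for late calls: on day 29 a participant would be asked about events as far back as day 1, 28 days earlier.

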7.5 Withdrawal criteria

Participants have the right to withdraw from the study at any time for any reason. The investigator also has the right to withdraw patients from the study for any reason. An excessive rate of withdrawals can render the study uninterpretable; therefore, unnecessary withdrawal of patients should be avoided.

Efforts will be made to continue to obtain 3-week follow-up data, even if the participant did not complete their sleep diary and with the permission of the patient. Participants who withdraw from the study will be offered the User Experience Questionnaire.

Should a patient decide to withdraw from follow up data collection, all efforts will be made to report the reason for withdrawal as thoroughly as possible. Participants who discontinue from the study will not be replaced. Clinical study team will complete the withdrawal form in the eCRF when participants chose to discontinue. Data already collected from a participant prior to withdrawal will be retained and used in the study.

7.6 Storage and Analysis of Clinical Samples

No biological samples will be collected in this study.

7.7 End of Study Definition

End of study will be defined as the last participant to complete their end of study visit (remote).

8 DIGITAL SLEEP DIARY

8.1 Description of digital sleep diary

The digital sleep diary has been designed by Closed Loop Medicine Ltd. This diary will be hosted, monitored, and managed by the digital sleep diary designers at Closed Loop Medicine. The digital sleep diary comes in the form of a patient-facing mobile phone application intended to be installed on the participant's smartphone. The application will be available in both iOS and Android, and we will establish a list of supported operating systems. A risk-based approach will be taken for supporting updates to these versions over the course of the study. All sleep data will be collected in the app. The sleep diary question set is consistent with previously published sleep diaries²⁴⁻²⁸ and will collect the following data daily from each participant:

- what time the patient got into bed last night
- what time did the patient try to go to sleep last night
- how long it took the patient to fall asleep
- how many times the patient woke up last night
- in total, how long the patient was awake during the night
- what was the patient's final wake-up time that morning
- how long the patient stayed in bed after waking up
- how did the patient rate their quality of sleep last night
- did something in particular affect the patient's sleep

No recommendations regarding diagnosis, intervention, treatment, or care planning will be made by the app.

8.2 Regulatory status of the digital sleep diary

The digital sleep diary used in this study is not a medical device.

8.3 Concomitant medication

Participants are permitted to continue taking existing concomitant medication, including sleep medication. During the three-week study period introduction of new sleep medication is not permitted.

8.4 Trial restrictions

There are no study restrictions.

8.5 Adherence to the digital sleep diary and study questionnaires

As compliance of data entry into the digital sleep diary is a secondary outcome, adherence to the digital sleep diary will not be monitored during the three-week study period. Adherence to the enrolment procedure required for downloading and setting up the digital sleep diary on participants smartphones will be assessed remotely by Closed Loop Medicine. If digital sleep diary has not been downloaded within three days of the participant receiving instructions to do so, the eCRF will send a reminder by email or text. If after another three days, the digital sleep diary has not been downloaded the clinical study team will attempt to call the participant to remind participant to download the app and determine if they require any assistance doing so. Compliance of data entry into the digital sleep diary during three-week study period will be assessed at the end of the three-week study period by Closed Loop Medicine.

Questionnaire adherence will be monitored by the clinical study team throughout the study period. Questionnaire reminders, at baseline and end of study, will be sent by email or text message to participants by the Qualtrics^{XM} platform. Reminder email or text messages will be sent up to three times, three days apart. If the end of study questionnaire set remains uncompleted, the clinical research team will remind the participant to complete the questionnaire during remote telephone consultation at day 21.

Non-compliance to the protocol study procedures will be documented by the investigator in the participant study files and site deviation log.

9 SAFETY REPORTING

9.1 Definitions

Term	Definition
Adverse Event	Any untoward medical occurrence in a study participant which does not necessarily have a causal relationship with the procedure involved.
Serious Adverse Event	
A serious adverse event is any untoward medical occurrence that:
 
 • results in death • is life-threatening • requires inpatient hospitalisation or prolongation of existing hospitalisation • results in persistent or significant disability/incapacity • consists of a congenital anomaly or birth defect 
Other 'important medical events' may also be considered serious if they jeopardise the participant or require an intervention to prevent one of the above consequences.
 
NOTE: The term "life-threatening" in the definition of "serious" refers to an event in which the participant was at risk of death at the time of the event; it does not refer to an event which hypothetically might have caused death if it were more severe.

9.2 Operational definitions for (S)AEs

The risks to participants enrolled in this observational study are considered very low.

All AEs and SAEs experienced during the three-week study period by participants enrolled in Stage 2 will be recorded in the eCRF and in the patients' medical records. AEs and SAEs can either be volunteered by the participant or detected by the clinical research team through physical examination or in the patients' medical notes.

Only SAEs that the Principal Investigator (PI) considers to be directly related to the digital sleep diary will be reported to the Sponsor via the EDC system.

9.3 Recording and reporting of SAEs

For each AE, the investigator must pursue and collect information to adequately determine the outcome of the AE and to assess whether it meets the classification criteria of an SAE. All SAEs considered to be directly related to the digital sleep diary, occurring from the time of participant consent to Stage 2 of the study to the conclusion of the 3-week observation period, must be reported to the Sponsor within 24 hours of awareness of the event by the PI. In the rare situation that the PI does not become immediately aware of the occurrence of a safety event, the PI must report the event within 24 hours of learning about it and record the time of awareness of the event.

For each SAE, the following information will be collected: full details in medical terms and case description, event duration (start and end dates, if applicable), action taken, outcome, seriousness criteria, and causality (i.e. relatedness to the digital sleep diary), in the opinion of the PI. Any change of condition or other follow-up information should be updated in the EDC system. The Sponsor should be notified as soon as it is available or at least within 24 hours of the information becoming available. Events will be followed up until the event has resolved or a final outcome has been reached.

9.4 Site Investigator Assessment

The PI is responsible for the care of the participant, or in his/ her absence an authorised clinician within the research team is responsible for assessment of any event for:

- Seriousness: assessing whether the event is serious according to above definitions (Section 9.1).
- Causality: assessing the causality of all serious adverse events/reactions in relation to use of the digital sleep diary according to the definition given.
- Severity: assessing the severity of the event according to the following terms and assessments. The intensity of an event should not be confused with the term "serious" which is a regulatory definition based on patient/event outcome criteria.
 - Mild: Some discomfort noted but without disruption of daily life
 - Moderate: Discomfort enough to affect/reduce normal activity
 - Severe: Complete inability to perform daily activities and lead a normal life.

The PI will ensure all SAEs are recorded and reported to the Sponsor within 24 hours of becoming aware of the event and provide further follow-up information as soon as available.

9.5 Sponsor Medical Assessment

The Sponsor's Chief Medical Officer (CMO) will oversee medical assessment of all reported SAEs. The CMO review all SAEs within 24 hours of receipt. This review will encompass seriousness and relatedness and be in accordance with the trial risk assessment and protocol as detailed in the Safety Monitoring Plan. As this observational study was deemed not to require Data Monitoring Committee

and / or Trial Steering Committee, the CMO is not required to report safety information to the independent oversight committees.

9.6 Notification of deaths

Only deaths that are assessed to be caused by use of the digital sleep diary app will be reported to the Sponsor. This report will be immediate from the point the assessment is made.

